2 STUDY OBJECTIVES

The overarching questions of our research are:

- 1) What are the mechanistic differences between patients who develop doxorubicin-induced cardiotoxicity and those who do not?
- 2) How do these differences drive cardiotoxicity?
- 3) Why do they drive cardiotoxicity in some patients and not others?
- 4) Can we predict which patients will develop cardiotoxicity before they become symptomatic?

In this pilot study we have identified three key aims, detailed below, that will allow us to generate preliminary data for the purpose of developing large-scale studies which will be focused towards answering these questions.

2.1 AIMS AND OBJECTIVES

2.1.1 Aim 1

To generate cardiomyocytes from patient-derived iPSCs.

Objectives

To achieve this, we will:

Version 2.24. Date: 1547/095/2022; IRAS:

Page 19 of 44

- Separate peripheral blood mononuclear cells (PBMCs) from patient blood samples.
- Reprogram PBMCs into iPSCs cells using the four Yamanaka transcription factors which will be introduced via Sendai-virus transduction or electroporation.
- Characterise and validate iPSC lines using microscopy, immunocytochemistry, and polymerase chain reaction (PCR).
- Develop reprogrammed iPSCs into patient-specific cardiomyocytes.
- Characterise and validate cardiomyocyte lines using microscopy, immunocytochemistry, PCR, and electrophysiology.

2.1.2 Aim 2

To characterise the mechanistic differences between patients with and without anthracycline-induced cardiotoxicity.

Objectives:

To achieve this, we will:

- Conduct proteomic profiling studies in cardiomyocytes generated from test subjects to detect short and long-term changes in protein expression levels.
- Characterise the electrical activity and calcium homeostasis of cardiomyocytes.
- Measure ionic currents, along with cardiac action potential to investigate morphological and pathophysiological changes in whole cell electrical signalling.
- Measure intracellular Ca²⁺ changes, intracellular ATP, mitochondrial function, and membrane potential.
- Analyse differences in mechanical beating behaviour between cardiomyocytes.

2.1.3 Aim 3

To Identify and characterise novel candidate biomarkers.

Objectives

To achieve this, we will:

- Use iPSCs to characterise biomarkers that can be readily validated within cells and secreted into media.
- Compare these to biomarkers found in blood obtained from patients.
- Compare the findings to the current method of detection of biomarkers at the participating hospital site (LHCH) to potentially identify new biomarkers through blood-based proteomics.

3 STUDY DESIGN

3.1 TYPE OF STUDY

This is a physiological case control study which aims to investigate the functional differences between iPSC-derived cardiomyocytes from two study groups.

Version 2.21. Date: 1517/095/2022; IRAS:

Page 20 of 44

3.2 DURATION

Funding duration for this study: 2 years

Recruitment duration for this study: 1 year

3.3 OUTCOME

Our primary outcome for this study is to generate iPSC-derived cardiomyocytes that are reproducible, amenable to experimental analysis, and that recapitulate the phenotype of the donor at the molecular and cellular level. This will not only allow us to begin addressing the research questions set out in this study of being able to better understand chemotherapy-induced cardiotoxicity, but will also enable us to use the technology to investigate other cardiac conditions and congenital defects.

Secondary outcomes include:

- Identifying a doxorubicin-specific signature in the cells derived from our cardiotoxicity subjects
 which signifies a distinct biological process that is absent in the control group. This would allow us
 a potentially significant insight into the mechanistic effects of doxorubicin-induced cardiotoxicity
 at a cellular and molecular level.
- Identifying candidate biomarkers that are of a functional relevance to doxorubicin-induced cardiotoxicity. Novel biomarker discovery could potentially offer an enhanced alternative to the current standard of risk stratification and cardiotoxicity detection in the clinic.
- Obtaining data that will support further investigations into different areas of future research such as the role of candidate biomarkers that could predict anthracycline-induced cardiotoxicity in other cancers and what their relationships are to cumulative drug dosing strategies for example.

These outcomes could eventually enable clinicians to better predict which patients will develop cardiotoxicity and how their care can be more appropriately managed. The research will deepen the understanding of doxorubicin-induced cardiotoxicity for health care professionals and service providers for integrated care. It will also assist in providing a better understanding of the options available for supporting chemotherapy patients at various stages of their care both during and following the completion of their treatment. It has the potential to improve the wellbeing and lives of patients as well as to improve how primary and secondary care services work together. The study will develop high quality data that will be disseminated with researchers, service users and health care professionals to create more effective practices in care.

3.4 STUDY SETTING

In this multicentre study we will recruit participants from three NHS outpatient services (LHCH, CCC, RLBUHT) with the help of clinicians and staff members working across these sites. Participants will be actively identified and recruited at all sites as follows:

- Liverpool Heart and Chest Hospital will identify and recruit doxorubicin-treated chemotherapy
 patients who do or do not exhibit cardiotoxicity as determined by the appropriate clinical coinvestigator (named on page vii of this document).
- Clatterbridge Cancer Centre and the Royal Liverpool and Broadgreen University Hospitals NHS Trust will refer doxorubicin-treated chemotherapy patients to LHCH for further examination.

Version 2.24. Date: 1547/095/2022; IRAS:

Page 21 of 44

LHCH provides specialist services in cardiothoracic surgery, cardiology, respiratory medicine and diagnostic imaging across Merseyside, Cheshire, North Wales, and the Isle of Man. Its outpatient department sees an estimated 70,000 patients a year and conducts a recently introduced consultant-led cardio-oncology clinic which see approximately 30 new referrals per month.

The Clatterbridge Cancer Centre NHS Foundation Trust is one of the UK's leading cancer centres and provides specialist cancer care across Cheshire, Merseyside and the surrounding areas including the Isle of Man. The centre provides non-surgical cancer care for blood cancers and solid tumours and operates specialist chemotherapy clinics in local district hospitals, including one of our participating sites - RLBUHT. The new Clatterbridge Cancer Centre, situated in central Liverpool alongside the University of Liverpool and Royal Liverpool University Hospital, will more greatly support recruitment opportunities of non-cardiotoxicity patients should it be necessary, and increase sample processing efficiency at the neighbouring University site.

The RLBUHT oncology services are world renowned and offer treatments for most types of cancer. The hospital works in collaboration with Clatterbridge and LHCH to deliver up-to-date care for cancer patients.

3.5 RECRUITMENT

3.5.1 Participant identification

Potential participants will be identified by the clinical co-investigators, as named on page 8 of this document, at LHCH. Identification of potential participants will be based on ejection fraction measurements as determined by the results of a retrospective 3D echocardiogram. Patients who have been referred to LHCH cardio-oncology clinic with suspected doxorubicin-induced cardiotoxicity will have received a 3D echocardiogram and blood-based biomarker test at the time of their outpatient appointment and either been diagnosed with cardiotoxicity or discharged back to their referring oncologist with negative test results. LHCH will approach those who fit the inclusion criteria from this selection of patients to be involved in the study. Once eligible cardiotoxicity participants have been identified at LHCH, non-cardiotoxicity subjects will be identified based on their retrospective test

Version 2.24. Date: 1547/095/2022; IRAS:

Page 22 of 44

results and matched to the cardiotoxicity subjects on tumour type, age, and treatment regime (including dosage and time frame). Non-cardiotoxicity subjects will be approached to take part as a control cohort by one of the named clinical co-investigators.

Eligible participants will be given basic information about the study by the co-investigator either during their outpatient appointment, over the phone, or by an invitation letter sent in the post. Patients who are interested in finding out more about the study will be given a Patient Information Sheet and the option to leave their telephone number for the clinical team to make contact, or to contact the clinical team themselves using the contact information given on the PIS.

Participants will not be recruited through Patient Identification Centres, disease registers, or through media advertising such as posters, leaflets, adverts, or websites. Participants will not receive any payment for participation in this study.

Due to the variation in reprogramming efficacy of stem cells, we may approach patients for a separate blood sample at a second clinical encounter. If patients do not want us to do this, they have the option to opt out at the time of consent and we will make a record of this in the site master file alongside their consent form; they will not be re-contacted. If, however, they are willing to provide a second sample, where possible we will take this during a routine outpatient appointment, however if this is not possible, we will arrange a research clinic appointment at LHCH.

A minority of patients may have already been consented prior to amending the protocol to allow us to re-approach patients for a second blood sample. In this instance we will contact the patient once via telephone and enquire whether they would be willing to give a second sample. If they do not want to give a second sample, we will make a note of this in the site master file and they will not be recontacted. If they are willing to provide a second sample, where possible we will take this during a routine outpatient appointment, however if this is not possible, we will arrange a research clinic appointment at LHCH. We will use an additional study consent form for the second sample and for the guestion '3. If required, I agree to be re-contacted once for further blood samples' we will ask them to write 'n/a'. This second consent form will be stored alongside their first consent form in the site master file.

3.6 SAMPLING

3.6.1 Size of sample

The maximum sample size for this pilot study at this stage will be 12 participants in total across all experimental groups (Figure 1). When selecting a sample size for this study we considered several factors including the nature of the study (i.e. a pilot study) and the financial feasibility of achieving our research aims at this stage. As this is a pilot study, we want to generate preliminary data that can support further funding applications that build on scientific evidence and eventually allow for larger sample sizes whilst still working realistically within the constraints of the study. Our approach is therefore to focus our efforts on obtaining a carefully planned smaller sample size which adequately represents significant aspects of the wider study population. This sample size is large enough to sufficiently address the primary research aims at the current stage and will provide valuable preliminary data to plan larger subsequent studies which will further address the overarching research questions.

Version 2.21. Date: 1517/095/2022; IRAS:

Page 23 of 44

Formatted: Indent: Left: 0.35 cm

[figure not shown]

Figure 1. Cancer patients with early-onset chronic cardiotoxicity and late-onset chronic cardiotoxicity will be recruited. Non-cardiotoxic patients will be matched to the cardiotoxic patients on tumour type, treatment regime and approximate age. For late-onset chronic cardiotoxic patients, noncardiotoxic patients will be recruited who have previously received the same treatment regime and not developed cardiotoxicity at the same point.

Version 2.21. Date: 1517/095/2022; IRAS:

Page 24 of 44

3.6.2 Sampling technique

The selection of participants will be purposive from a population of outpatients across three NHS hospital trust sites. This method of sample selection has been chosen to allow us to obtain information from a limited number of individuals within specific groups of interest (i.e. doxorubicin-treated patients who do and do not exhibit cardiotoxicity). Representative samples of interest will be selected by an experienced authority at each participating site. Whilst non-randomised sampling such as this may allow for selection bias, it also limits the possibility of sampling error, and data generated from the study will enable us to conduct larger studies where a better representation of the entire study population will be achievable through access to larger sampling numbers.

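### Section 3.6.2 wrongly says purposive sampling limits sampling error, and no rule governs the choice among several eligible matched controls

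*Protocol*

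**What the plan says.** Section 3.6.2 of the protocol sets the method: "The selection of participants will be purposive from a population of outpatients across three NHS hospital trust sites". The reason given is practical: "This method of sample selection has been chosen to allow us to obtain information from a limited number of individuals within specific groups of interest". On who chooses, it says: "Representative samples of interest will be selected by an experienced authority at each participating site". It then weighs the method's drawback against a supposed benefit: "Whilst non-randomised sampling such as this may allow for selection bias, it also limits the possibility of sampling error".

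Section 3.5.1 describes how controls are found. Patients referred to the cardio-oncology clinic with suspected doxorubicin cardiotoxicity already have an echocardiogram and biomarker result. Once cases are identified, controls are found from their past results and matched to the cases on tumour type, age and treatment regime, the last including dose and timing. Then: "Non-cardiotoxicity subjects will be approached to take part as a control cohort by one of the named clinical co-investigators". Neither section says which patient is approached when more than one meets the matching criteria.

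Section 3.6.1 caps the study at 12 participants, and the caption of Figure 1 divides the cases into early-onset and late-onset groups. Section 6.2.2.7 compares cardiotoxicity and non-cardiotoxicity samples with a two-tailed t test.

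**The concern.** Two things are wrong, and they are linked.

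First, the justification is false. Sampling error is the chance variation that comes from observing few donors out of many. It is set by donor-to-donor variability and the number of donors. Picking donors by judgement changes neither in a useful way, and it removes the probability basis on which the error would be estimated. Section 3.6.2 therefore accepts a real cost (selection bias) in return for a benefit that is not there.

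Second, the cost is partly avoidable. Choosing the groups purposively is reasonable. Within a group, though, and after matching, the person who picks the donor knows the clinical results and has no rule to follow. If the pick leans on any trait related to the laboratory read-outs, the case-control difference shifts for reasons unrelated to cardiotoxicity. At stake are the secondary comparisons and the preliminary data that section 3.6.1 intends for planning larger studies. An analysis plan cannot repair this later, because unrecorded selection leaves nothing to adjust for.

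**Working it through.** The protocol derives no figure here: 12 rests on pilot status and funding, so there is no calculation to reproduce.

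**Inputs from the protocol.** Maximum 12 participants (3.6.1); matching on tumour type, age and regime (3.5.1); two-tailed t test (6.2.2.7).

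**Assumptions.** A 6 v 6 split, with 8 v 4 and 3 v 3 as a range (Figure 1 is not shown); *m* eligible controls per case; correlation *r* between the trait that guides the pick and the read-out; the extreme match always taken; no true difference; unit donor SD.

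**Step 1: what sets sampling error.** SE of a difference = SD × √(1/n₁ + 1/n₂); 95% half-width = t(0.975, n₁+n₂−2) × SE.

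- 6 v 6: √(1/6 + 1/6) = 0.577; 2.228 × 0.577 = 1.29 SD.
- 8 v 4: √(1/8 + 1/4) = 0.612; 2.228 × 0.612 = 1.36 SD.
- 3 v 3: √(1/3 + 1/3) = 0.816; 2.776 × 0.816 = 2.27 SD.

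Only variability and numbers enter. How the donors were picked does not.

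**Step 2: what judgement selection changes.** Expected shift in the control mean = *r* × E(maximum of *m* standard normals), with E = 0 (m = 1), 0.56 (m = 2), 0.85 (m = 3), 1.16 (m = 5).

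- m = 3: 0.3 × 0.85 = 0.25 SD; 0.5 × 0.85 = 0.42 SD.
- m = 5: 0.3 × 1.16 = 0.35 SD; 0.5 × 1.16 = 0.58 SD.

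**Step 3: simulation of 6 v 6 t tests (100,000 runs per setting).**

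| m | r | Bias, absolute (SD) | SD of difference | RMSE | Type I error |
|---|---|---|---|---|---|
| 1 | any | 0 | 0.58 | 0.58 | 5% |
| any | 0 | 0 | 0.58 | 0.58 | 5% |
| 2 | 0.3 | 0.17 | 0.57 | 0.60 | 6% |
| 2 | 0.5 | 0.28 | 0.57 | 0.63 | 7% |
| 3 | 0.3 | 0.25 | 0.57 | 0.62 | 7% |
| 3 | 0.5 | 0.42 | 0.56 | 0.71 | 11% |
| 5 | 0.3 | 0.35 | 0.57 | 0.67 | 9% |
| 5 | 0.5 | 0.58 | 0.56 | 0.80 | 16% |

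A random pick among the same matches gives bias 0, SD 0.577 and RMSE 0.577. Trait-based picking trims the SD of the difference from 0.577 to 0.56-0.57, by about 3% at most in this table, while total error rises. That is the nearest thing to the claimed benefit, and the bias outweighs it.

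**The case against.** Several counter-arguments are sound and limit the point.

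- **Rationale.** A reader might infer that donors are hand-picked because of the sampling-error claim. They are not: the direct reason in 3.6.2 is to reach specific groups with few people. The false clause is the counterweight to the admitted bias.
- **Disclosure.** The same sentence openly admits selection bias and leaves better representation to larger studies. Nothing is concealed.
- **Representativeness.** One might see a contradiction with 3.6.1, which speaks of a "carefully planned smaller sample size which adequately represents significant aspects of the wider study population". Adequate coverage of some aspects now and better coverage of the whole population later can both be true.
- **Comparator.** Controls chosen under 3.5.1 are matched-regime patients without cardiotoxicity, so they are the comparator that the objectives name.
- **Width of the interval.** The ±1.29 SD is the same under random choice. It shows that the claim is false, not that purposive choice does harm.
- **Unknown pool.** The protocol gives no number of matches per case. Section 3.4 says the hospital "conducts a recently introduced consultant-led cardio-oncology clinic which see approximately 30 new referrals per month", but that counts all referrals, not matched doxorubicin patients with normal function. With *r* = 0.1, type I error stays between 5% and 6% for 2 to 10 matches.
- **Primary outcome.** Section 3.3 makes the primary outcome the generation of usable cardiomyocytes, which this bias does not touch.

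What remains is that the clause is wrong and that no rule exists where there is a choice. The instruction in 3.5.1 to approach those who meet the inclusion criteria does not settle it, because the cap of 12 and the matching require a selection whenever more patients qualify.

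**Conclusion.** The point holds. The sampling-error clause in 3.6.2 is incorrect whatever is assumed. The free choice among eligible matches is an avoidable source of bias in the secondary case-control comparisons and in the effect sizes carried into later planning.

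Its size is illustrative only: no inflation with one match or a trait unrelated to the read-out, and about 7-16% type I error with 3-5 matches and correlations of 0.3-0.5, if the extreme match is always taken in a 6 v 6 design. Larger assumed pools give larger figures, but nothing in the protocol supports treating them as expected.

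A reader might also infer that the results will be too favourable. The protocol does not support a direction. Taking the fittest control would widen the contrast, whereas taking the control most like the case would narrow it and could hide a real difference.

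**What to change.** In section 3.6.2, delete the clause about sampling error. Keep the purposive choice of groups and the matching in 3.5.1, and add a rule along these lines:

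- Within each onset group (early, late), eligible cases are approached consecutively. Doing this by group keeps both groups filled, which simple attendance order would not guarantee.
- Where a case has more than one eligible matched control, the clinical team lists them all and approaches them in computer-generated random order until one consents. With a single match there is nothing to randomise.
- The numbers eligible and approached are logged for each case.
- The protocol states that referral bias (controls come from patients referred with suspected cardiotoxicity) and consent bias remain, since random order does not remove them.

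Because the Figure 1 caption allows approximate age matching, a nearest-match rule fixed in advance would be a defensible alternative to random order. Either closes the gap.

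The cost is a few sentences in an amendment and a spreadsheet random number, with no extra patients, tests or staff. The clinician loses discretion over which eligible match to approach, a small downside.

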3.6.3 Sample collection

A venous blood sample will be taken from the antecubital area of the arm by a health care assistant or research nurse with experience of the venepuncture procedure. Samples will be collected in blood tubes which are appropriate for the end-point assay and used to isolate peripheral blood mononuclear cells and plasma. Once the sample has been drawn, to best preserve cell integrity, it will be maintained at room temperature (15-25°C) and processed within 24 hours of collection. Where possible, research samples will be taken with clinical samples during outpatient appointments to minimise the inconvenience to the participant. Where this is not possible, a research clinic will be arranged at LHCH to sample participants that have no pre-scheduled outpatient appointments.

3.6.4 Sample transfer and processing

Following sampling at LHCH, all blood tubes will primarily be stored under the relevant conditions in the research laboratory at LHCH before being collected on the same day by the study's designated research assistant and transferred to the University of Liverpool's main campus for processing. If a participant is sampled at one of the study's other participating hospital sites (CCC and RLBUH), which are situated adjacently to the University of Liverpool's main campus, then those samples will be collected immediately by the study's designated research assistant and transferred across to the University of Liverpool for processing. All samples transferred to the University of Liverpool will be documented on a transfer log and their end-location will be recorded. All samples will be processed by the study's research assistant at the University of Liverpool in the Sherrington Building's primary tissue culture suite.

3.6.5 Sample storage and tracking

After processing, surplus peripheral blood mononuclear cells from all participants will be frozen for long-term storage at -150°C under HTA guidelines. Plasma and nucleic acid samples will also be stored from all participant samples and will not be considered 'relevant material' under the HTA Act 2004. All samples (cells, plasma, nucleic acids) will be stored at the Clatterbridge Cancer Centre-Liverpool under the custodianship of the project's CI. Sample processing will be logged on a secure Microsoft Excel database and the details will be replicated in a linked logbook which will be kept in a secure drawer in a locked office at the University of Liverpool. The CI and research assistant will have access to the samples and access to the secure database which will allow for monitoring of their location during storage and subsequent use. No whole blood will be stored. Samples may be stored for future unspecified research with ethical approval.

Version 2.21. Date: 1517/095/2022; IRAS:

Page 25 of 44

Version 2.24. Date: 1547/095/2022; IRAS:

I

Page **26** of **44**

